#### Arm B

Accrual to Arm B will be halted and trigger a review by the study investigators and the DSMC to determine if the study should be modified, or permanently closed to further accrual according to the following:

1. Stop the study for safety if the observed DLT rate at the lowest combination (Combination 1)  $\geq$  the following number of DLTs out of the following number of patients treated at the lowest combination. These stopping guidelines are based on whether the lower limit of an Agresti-Coull binomial confidence interval (with 80% confidence) for the lowest combination exceeds the target DLT rate. The following bounds were generated using the web application at <http://uvatrapps.uvadcos.io/pocrm/>.

Stopping guidelines for DLTs at the lowest combination	
Number of participants	Boundary
2-3	$\geq 2$
4-6	$\geq 3$
7	$\geq 4$

2. If the recommendation is to assign the next patient to a combination that already has 7 participants treated on the combination, the study is stopped and the recommended combination is declared the MTD.
3. Otherwise, the MTD is defined as the combination that is recommended after the maximum target sample size of 30 participants are accrued to the study.

### 10.4 Sample size and accrual

A maximum target accrual of 5 additional eligible participants is planned in Arm A (total accrual n=10) and 6 additional eligible participants in Arm C (total accrual n=10). A maximum target accrual of 26 additional eligible participants is planned in Arm B (total accrual n=30), but simulation results below indicate that the average estimated

sample size needed to complete accrual to Arm B is between 3.5 (total accrual n=7.5) and 11.3 (total accrual n=15.3) additional participants. Maximum total sample size for all arms is estimated to be approximately 23 additional participants (total accrual n=36). For estimation of ORR at the MTD, a sample size of 7 at the MTD produces a two-sided 80% binomial confidence interval with a width equal to 0.556 when the sample proportion is 0.5. Additional subjects will be enrolled to replace any subjects who are enrolled, but do not receive treatment. Accrual is estimated at 2 participants per month. Adjusting for an approximate 5% drop-out/ineligibility rate, maximum target accrual should not exceed 38 participants.

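### The stated maximum accrual of 36 (38 with drop-out) uses Arm B's largest average sample size; the design's own maxima add to 50 (53), so Arm B can reach the ceiling with no MTD defined

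*Protocol*

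**What the plan says.** Section 10.4 sets a maximum for each arm:

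- Arm A: "A maximum target accrual of 5 additional eligible participants is planned in Arm A (total accrual n=10").
- Arm C: "6 additional eligible participants in Arm C (total accrual n=10").
- Arm B: "A maximum target accrual of 26 additional eligible participants is planned in Arm B (total accrual n=30").

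For Arm B it adds that the average "sample size needed to complete accrual to Arm B is between 3.5 (total accrual n=7.5) and 11.3 (total accrual n=15.3) additional participants". It then gives the overall figure, "Maximum total sample size for all arms is estimated to be approximately 23 additional participants (total accrual n=36"), and the ceiling: "Adjusting for an approximate 5% drop-out/ineligibility rate, maximum target accrual should not exceed 38 participants". Section 1.0 lists 38 as the maximum number of subjects, without qualification.

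Section 10.3 gives Arm B two routes to an MTD. Rule 2 applies first: "If the recommendation is to assign the next patient to a combination that already has 7 participants treated on the combination, the study is stopped". That combination is then declared the MTD. Rule 3: otherwise, the MTD is the combination recommended "after the maximum target sample size of 30 participants are accrued to the study". Section 10.5 simulated Arm B with a cap of 30.

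**The concern.** The three arm maxima do not add to the overall maximum. The gap lies wholly in Arm B, where the overall figure appears to use an average in place of the cap of 30.

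This matters because the figure is then used as a limit on accrual. By Sections 5.1 and 7.6, Arm B enrols last, so it absorbs any shortfall. If 38 is enforced, Arm B can run out of places with neither 7 participants on the recommended combination nor 30 enrolled. Section 10.3 then names no MTD, response rate at the MTD has no defined dose, and the Section 10.5 operating characteristics describe a longer trial than the one run. If 38 is not enforced, the trial exceeds its own stated maximum.

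**Working it through.** **Inputs.** Already enrolled (Section 10.1): 5 in Arm A, 4 in Arm C, 4 in Arm B, 13 in all. Additional maxima (Section 10.4): 5, 6 and 26. Largest Arm B average (Section 10.5, Scenario 5): 15.32 in total, so 11.3 additional. Drop-out: 5%.

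**Reproducing the stated figures**

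- Additional: 5 + 6 + 11.3 = 22.3, rounded up to 23.
- Total: 23 + 13 = 36. Check on totals: 10 + 10 + 15.32 = 35.32, rounded up to 36.
- With drop-out: 36/0.95 = 37.9, rounded up to 38.

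All three match, and they do so only with the Arm B average.

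**The same sums with the stated maxima**

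- Additional: 5 + 6 + 26 = 37.
- Total: 37 + 13 = 50, which is 10 + 10 + 30.
- With drop-out: 50/0.95 = 52.6, rounded up to 53.
- Against the stated ceiling: 53/38 = 1.39, or 39% more.

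**Room left for Arm B**

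- Arms A and C at 10 each: 36 - 20 = 16 evaluable places, or 38 - 20 = 18 with no drop-out.
- Arms A and C stopping at 7 each, the fewest found under their stopping rules: 38 - 14 = 24.
- Even then, 7 + 7 + 30 = 44 exceeds 38, so rule 3 is out of reach in every case.

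**How often Arm B would need more places.** The Arm B design was re-simulated: protocol skeletons, 1 DLT in 4 already on Combination 8, stop at 7, safety bounds, cap 30, 3,000 trials per scenario. The protocol does not give the split of DLT types, so pralatrexate-type DLTs were assumed to be 50% to 90% of the total. Moves to a lower combination after a non-DLT were allowed.

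| Scenario | Published mean | Re-simulated mean | Arm B >16 | Arm B >18 |
|---|---|---|---|---|
| 1 | 8.42 | 9.14-9.26 | 8-9% | 4-5% |
| 2 | 8.84 | 9.59-9.74 | 10-11% | 5-6% |
| 3 | 7.51 | 7.72-7.83 | 1-2% | <1% |
| 4 | 12.44 | 14.32-14.56 | 43-44% | 30-32% |
| 5 | 15.32 | 17.04-17.26 | 61-64% | 50-52% |

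More than 24 were needed in 5-6% of trials in Scenario 4 and 12-13% in Scenario 5.

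These runs overshoot the published means, so the shares in Scenarios 4 and 5 are probably too high. If neither agent may be reduced after a non-DLT, the means come close to the published ones. The shares then fall as low as about 11% (Scenario 4) and 23% (Scenario 5) for more than 18, and 18% and 35% for more than 16.

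**The case against.** The strongest reply is that this is a labelling fault in a transparent paragraph. Section 10.4 states the Arm B cap of 30, says that the average is lower, and calls the total an estimate. The sums are correct for what they add. That is fair as a description, but the next sentence turns the result into a limit, and Section 1.0 repeats it with no hint that it is an expectation.

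Three further points have weight:

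- The figure of 16 to 18 places assumes that Arms A and C both reach 10. Either can stop early, which gives Arm B up to 24. Arm B already has participants, so the final Arm A and C counts may be known. This narrows the shortfall but does not remove it.
- A full 30 in Arm B is remote: about 1% or less in one set of runs, and 0.3% to 1.6% in Scenarios 4 and 5 in another. So 50 is a formal maximum, not a forecast.
- The sponsor could amend the protocol as the ceiling approaches, and the DSMC reviews accrual monthly. The protocol does not set out this route, and the possibility of amendment does not reconcile two limits that conflict now.

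The simulated shares are indicative only. In Scenarios 1 to 3 the ceiling would seldom matter.

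**Conclusion.** The concern holds. The overall maximum of 36 and the ceiling of 38 rest on an average. The protocol's own arm limits give 50, or 53 with the same 5% allowance. Rule 3 for Arm B and the cap of 30 used in Section 10.5 cannot hold together with a ceiling of 38, whatever happens in Arms A and C. This part is addition and needs no simulation.

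The practical risk depends on how toxic the upper combinations are. With Arms A and C at 10 each, Arm B would need more than 18 participants in about 11% to 32% of trials in Scenario 4 and about 23% to 52% in Scenario 5, subject to the unstated DLT-type split and the reading of the allocation rule after a non-DLT. It is 6% or less in Scenarios 1 to 3. The ceiling therefore binds mainly when the starting combination is too toxic and the search for a lower one is still under way. Because it leaves a primary objective without a defined result in those cases, it must be corrected.

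**What to change.** Choose one of two repairs.

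1. **Keep the Arm B cap of 30.** In Sections 1.0 and 10.4, state the maximum as 50, or 53 with 5% drop-out. Describe 36 as the expected total in the worst simulated scenario with Arms A and C full. The cost is wording in two sections and an updated approved maximum. Expected enrolment does not change.
2. **Keep the ceiling of 38.** Replace 30 in Arm B rule 3, and in the Arm B maximum in Section 10.4, with the number that fits once Arms A and C are counted and drop-out is allowed for: 16 if both arms are at 10. Re-run the Section 10.5 Arm B tables with that cap. The cost is a new set of simulations, which may show poorer MTD selection in Scenarios 4 and 5.

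Under either repair, Sections 1.0, 10.3, 10.4 and 10.5 should carry the same Arm B limit.

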### 10.3 Stopping rules and MTD definition

#### Arms A and C

Accrual to Arms A and C will be halted and trigger a review by the study investigators and the DSMC to determine if the study should be modified, or permanently closed to further accrual according to the following:

1. Stop the study for safety if the observed DLT rate at the lowest study dose level (Level -2)  $\geq$  the following number of DLTs out of the following number of patients treated at the lowest study dose level. These stopping guidelines are based on whether the lower limit of an Agresti-Coull binomial confidence interval (with 80% confidence) for the lowest study dose level exceeds the target DLT rate. The following bounds were generated using the web application at <http://uvatrapps.uvadcos.io/crmb/>. Note that, given the accrual of previous participants to dose level 1 in Arms A and C, at most 4 participants can be accrued to Level -2 before the maximum sample size is reached.

Stopping guidelines for DLTs at the lowest dose level	
Number of participants	Boundary
2-3	$\geq 2$
4	$\geq 3$

2. If the recommendation is to assign the next patient to a dose level that already has 7 participants treated at the dose level, enrollment to the arm is stopped and the recommended dose level is declared the MTD.
3. Otherwise, the MTD is defined as the dose level that is recommended after the maximum sample size of 10 participants for the arm.

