## 10.5 Operating characteristics

### Arms A and C

Simulations were run to display the performance of the design characteristics in Arms A and C using the R statistical programming language. For each scenario, 5000 simulated trials were run using a random seed of 322348. The confidence level used to define the safety stopping guidelines was 80%. Each table reports the true DLT probability at each dose level, the percentage of trials in which each dose level was recommended as the MTD, the average number of participants treated at each dose level, and the percentage of trials stopped early for safety. The results displayed in the following tables were based upon a maximum target accrual of 10 subjects.

Operating characteristics in Arm A for the continual reassessment method with cohorts of size 1. Bold font indicates the level that is the MTD corresponding to a target DLT rate of 25%. Previously, there were 5 participants accrued (1 observed DLT) on dose level 3. Sample size for each scenario is n=10 total (previous plus additional) participants.					
Scenario		Dose level 1	Dose level 2	Dose Level 3	% stopped for safety
1	True DLT prob:	0.05	0.15	0.25	0.0
	MTD selection %	5.7	22.6	71.7	
	Avg # of patients	0.1	0.6	9.3	
2	True DLT prob:	0.15	0.25	0.40	0.24
	MTD selection %	18.9	36.2	44.7	
	Avg # of patients	0.3	1.0	8.7	
3	True DLT prob:	0.25	0.40	0.55	1.24
	MTD selection %	41.2	34.0	23.5	
	Avg # of patients	0.6	1.4	8.0	

Operating characteristics in Arm C for the continual reassessment method with cohorts of size 1. Bold font indicates the level that is the MTD corresponding to a target DLT rate of 25%. Previously, there were 4 participants accrued (1 observed DLT) on dose level 3. Sample size for each scenario is n=10 total (previous plus additional) participants.					
Scenario		Dose level 1	Dose level 2	Dose Level 3	% stopped for safety
1	True DLT prob:	0.05	0.15	0.25	0.0
	MTD selection %	6.9	3.1	62.1	
	Avg # of patients	0.3	1.2	8.5	
2	True DLT prob:	0.15	0.25	0.40	0.52
	MTD selection %	23.6	43.7	32.2	
	Avg # of patients	0.7	1.8	7.5	
3	True DLT prob:	0.25	0.40	0.55	2.24
	MTD selection %	50.1	35.4	12.2	

	Avg # of patients	1.5	2.0	6.5	
--	-------------------	-----	-----	-----	--

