## 10.6 Data Analysis Plan

All subjects who are put on-study will be assessed for inclusion in the final report. All subjects who receive any protocol treatment will be monitored for adverse events. Adverse events will be described and coded based upon the NCI CTCAE v5.0. A DLT is defined in Section 5.3. Occurrence of DLTs will contribute to escalation and stopping decisions. Adverse events will be summarized by frequency and magnitude of event. Incidence of DLTs will be monitored against the safety bounds above. The bounds are non-binding, and provide a guideline that may result in study modification or closure. At study conclusion frequency, proportion and severity of adverse events, and DLTs by study dose level, as well as by arm, will be tabulated. Point estimates and 90% Agresti-Coull binomial confidence intervals will be calculated for dichotomous endpoints (AEs, DLTs, overall response). For longitudinal measurements (i.e., immunologic and pharmacodynamic markers; see Sections 3 and 5.6), graphical methods will be used to display the data and exploratory repeated measures models will be used to describe changes over time. For continuous variables (i.e., duration of response), means, medians, and variability measures will be summarized with point estimates and 95% confidence intervals. PFS and OS distributions will be estimated by the product limit method of Kaplan and Meier.

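### Section 10.4's only precision figure for ORR at the MTD is not the interval planned in 10.6, and its n of 7 cannot be reached in Arms A and C if the MTD lies below Level 1

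*Protocol*

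**What the plan says.** Section 10.1 makes ORR at the estimated MTD a primary objective of every arm. The only statement of how precisely it will be estimated is in 10.4: "a sample size of 7 at the MTD produces a two-sided 80% binomial confidence interval with a width equal to 0.556", for a sample proportion of 0.5. The interval method is not named there. Section 10.6 specifies the analysis: "Point estimates and 90% Agresti-Coull" is followed by "binomial confidence intervals will be calculated for dichotomous endpoints (AEs, DLTs, overall response", so overall response is covered.

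The number 7 is the stopping number in 10.3. Enrolment to an arm ends when the next patient would go to "a dose level that already has 7 participants treated at the dose level". Otherwise, in Arms A and C, the MTD is whatever level is recommended after 10 participants, with no minimum number treated at it. Section 10.4 plans 5 further participants in Arm A and 6 in Arm C, each to a total of 10. Section 10.3 places the earlier participants of both arms on Level 1 and adds that "at most 4 participants can be accrued to Level -2 before the maximum sample size is reached".

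On Arm C the protocol gives two histories. Section 10.1 reports 2 DLTs in the first 4 subjects and sends the next one to Level -1. The Arm C table heading in 10.5 reads "Previously, there were 4 participants accrued (1 observed DLT) on dose level 3" (dose level 3 there is Level 1 in 10.1).

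**The concern.** A planning figure should describe the interval that will be reported, at a sample size the design can deliver. Here it differs from the planned analysis in confidence level and in method. It also rests on an n that Arms A and C can reach only if Level 1 is the MTD. A reader of 10.4 would take n=7 and 0.556 as the precision available in all three arms. In Arms A and C the dose carried forward may rest on a handful of responses, or on none. At stake is how ORR at the MTD is described; dosing, the estimand and the planned analysis are not affected.

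**Working it through.** **1. The stated figure.** Inputs from 10.4: n=7, proportion 0.5 (x=3.5), 80% two-sided. Clopper-Pearson limits are the 0.10 quantile of Beta(3.5, 4.5) = 0.2221 and the 0.90 quantile of Beta(4.5, 3.5) = 0.7779. The width is 0.5559, which is the printed 0.556. Other 80% intervals do not give it: Agresti-Coull 0.436, Wilson 0.436, Wald 0.484, Jeffreys 0.443.

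**2. The planned interval.** For 90% Agresti-Coull, z = 1.645 and z² = 2.706. At proportion 0.5 the width is 2z·√(0.25/(n+z²)) = z/√(n+z²). At n=7 this is 1.645/√9.706 = 0.528.

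| n | 7 | 6 | 5 | 4 | 3 | 2 | 1 |
|---|---|---|---|---|---|---|---|
| Width at 0.5 | 0.53 | 0.56 | 0.59 | 0.64 | 0.69 | 0.76 | 0.85 |

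For a given n, 0.5 is the widest case. From the same formula, before any truncation at 0 or 1, the width is 0.586 for 0/3, 0.678 for 1/3, 0.510 for 0/4 and 0.546 for 1/5.

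**3. Places left.** Arm A: 10 − 5 = 5. Arm C: 10 − 4 = 6. Neither allows 7 below Level 1. Only untreated participants are replaced (10.4), so the number treated does not rise.

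**4. What the CRM allows.** Rules from 10.2: skeleton 0.08/0.15/0.25, target 25%, cohorts of one, no skipping, no escalation after a DLT, no de-escalation without one. For Level -2, subtraction is enough:
- Arm A restarts at Level 1, so at least one more patient is used there and one at Level -1: 10 − 5 − 1 − 1 = 3.
- Arm C from 1 DLT in 4 also restarts at Level 1: 10 − 4 − 1 − 1 = 4.
- Arm C from 2 DLTs in 4 restarts at Level -1: 10 − 4 − 1 = 5.

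For Level -1, enumerating every DLT path gives the same maxima at a declared MTD:

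| Start | Level 1 (with stop at 7) | Level -1 | Level -2 |
|---|---|---|---|
| Arm A, 1 in 5 | 7 | 3 | 3 |
| Arm C, 2 in 4 (10.1) | 6 | 5 | 5 |
| Arm C, 1 in 4 (10.5) | 7 | 4 | 4 |

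The maxima below Level 1 are the same with or without the stop at 7.

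**5. How often this arises.** Share of trials declaring an MTD below Level 1, in Scenarios 1/2/3 of 10.5:
- Printed tables, Arm A: 5.7+22.6 = 28.3%, 18.9+36.2 = 55.1%, 41.2+34.0 = 75.2%.
- Printed tables, Arm C: 37.9%, 67.3%, 85.5%. The first is 100 − 62.1, because the printed row adds to only 72.1.
- Enumeration with the stop at 7: Arm A 9.0/21.4/36.7%; Arm C 23.1/45.6/63.1% from 1 in 4, or 70.3/84.7/83.5% from 2 in 4.

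The printed tables do not apply the stop: the heading says "Sample size for each scenario is n=10 total (previous plus additional) participants", and Arm A averages up to 9.3 patients on the top level. With the stop, the declared MTD has no treated patients in 0.7/2.3/4.4% of Arm A trials and 1.1/3.0/4.6% of Arm C trials from 1 in 4.

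**6. Check on the enumeration.** Without the stop it gives Level 1 selection of 72.2/45.4/22.1% in Arm A (printed 71.7/44.7/23.5) and 62.8/33.3/12.4% in Arm C from 1 in 4 (printed 62.1/32.2/12.2). It does not reproduce the safety-stop column. In Scenarios 2/3 it gives 0.6/3.4% in Arm A (printed 0.24/1.24) and 1.6/7.5% in Arm C (printed 0.52/2.24), up to about three times the printed rates. The shares in step 5 are therefore approximate; the maxima in step 4 do not depend on them. The safety boundary at 5 patients on Level -2 is not listed in 10.3 and was taken as 3, which the 80% Agresti-Coull rule gives.

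**The case against.** The sentence in 10.4 is conditional and true: it says what 7 patients would give, not that every arm will have 7. Using one interval for planning and another for reporting is untidy, but here the planned interval is the narrower one. Section 10.3 already tells the reader that Level -2 cannot reach 7. Arms A and C may also be finished: 7.6 opens Arm B only after both are complete, and 10.1 already reports four Arm B subjects. All of this stands, and it keeps the point minor. It does not remove it, because 10.4 still plans 5 and 6 more participants in those arms and offers no other precision figure for a primary objective.

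Three stronger readings are tempting, and the protocol does not support them. First, that an 80% level makes the plan look more precise than it is: at n=7 the reverse holds, 0.528 against 0.556. Second, that the reported interval must be at least 0.69 wide in Arm A: that width belongs to n=3 at proportion 0.5, and extreme response proportions give less. Third, that the "at most 4" note in 10.3 is wrong throughout. It is an upper bound, which Arm A's 3 satisfies; it conflicts only with the 2-in-4 start in Arm C, where the maximum is 5.

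**Conclusion.** The concern holds as a minor point of internal consistency. The 0.556 is computed correctly, but for an interval that 10.6 does not plan. In Arm B, where 7 is attainable, that mismatch is the only issue. In Arms A and C the n of 7 is out of reach whenever the MTD is below Level 1: at most 3 patients in Arm A, and 5 or 4 in Arm C. At proportion 0.5 the planned widths at those maxima are 0.69, and 0.59 or 0.64. They are wider with fewer patients and narrower at extreme proportions, and no interval exists if nobody was treated at the declared MTD. At Level 1 the figure is fair: Arm A can reach 7, and Arm C can reach 7 from the 1-in-4 start or 6 from the 2-in-4 start. The maxima assume that 10.2 is applied as written. How often they matter depends on the scenario, on the stop at 7 and on which Arm C history is right.

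**What to change.** Replace the precision sentence in 10.4 with wording such as: ORR at the MTD will be reported with a 90% Agresti-Coull interval; at a sample proportion of 0.5 its width is 0.53 with 7 participants, 0.56 with 6, 0.59 with 5, 0.64 with 4, 0.69 with 3, 0.76 with 2 and 0.85 with 1. In Arms A and C fewer than 7 participants, possibly none, will have been treated at an MTD below Level 1; if none were, no ORR interval at the MTD will be given.

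Reconcile the Arm C DLT count between 10.1 and the 10.5 table heading before stating what that arm can reach, then align the note in 10.3 on Level -2. If Arms A and C are already complete, give the actual number treated at the MTD and its width instead.

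The cost is wording only. The stated precision becomes slightly better at 7, practically unchanged at 6 and less favourable at 5 or fewer.

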## 10.5 Operating characteristics

### Arms A and C

Simulations were run to display the performance of the design characteristics in Arms A and C using the R statistical programming language. For each scenario, 5000 simulated trials were run using a random seed of 322348. The confidence level used to define the safety stopping guidelines was 80%. Each table reports the true DLT probability at each dose level, the percentage of trials in which each dose level was recommended as the MTD, the average number of participants treated at each dose level, and the percentage of trials stopped early for safety. The results displayed in the following tables were based upon a maximum target accrual of 10 subjects.

Operating characteristics in Arm A for the continual reassessment method with cohorts of size 1. Bold font indicates the level that is the MTD corresponding to a target DLT rate of 25%. Previously, there were 5 participants accrued (1 observed DLT) on dose level 3. Sample size for each scenario is n=10 total (previous plus additional) participants.					
Scenario		Dose level 1	Dose level 2	Dose Level 3	% stopped for safety
1	True DLT prob:	0.05	0.15	0.25	0.0
	MTD selection %	5.7	22.6	71.7	
	Avg # of patients	0.1	0.6	9.3	
2	True DLT prob:	0.15	0.25	0.40	0.24
	MTD selection %	18.9	36.2	44.7	
	Avg # of patients	0.3	1.0	8.7	
3	True DLT prob:	0.25	0.40	0.55	1.24
	MTD selection %	41.2	34.0	23.5	
	Avg # of patients	0.6	1.4	8.0	

Operating characteristics in Arm C for the continual reassessment method with cohorts of size 1. Bold font indicates the level that is the MTD corresponding to a target DLT rate of 25%. Previously, there were 4 participants accrued (1 observed DLT) on dose level 3. Sample size for each scenario is n=10 total (previous plus additional) participants.					
Scenario		Dose level 1	Dose level 2	Dose Level 3	% stopped for safety
1	True DLT prob:	0.05	0.15	0.25	0.0
	MTD selection %	6.9	3.1	62.1	
	Avg # of patients	0.3	1.2	8.5	
2	True DLT prob:	0.15	0.25	0.40	0.52
	MTD selection %	23.6	43.7	32.2	
	Avg # of patients	0.7	1.8	7.5	
3	True DLT prob:	0.25	0.40	0.55	2.24
	MTD selection %	50.1	35.4	12.2	

	Avg # of patients	1.5	2.0	6.5	
--	-------------------	-----	-----	-----	--

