## **10.0 STATISTICAL CONSIDERATIONS**

### **10.1 Study Design**

This is a Phase Ib study evaluating the safety and efficacy of pembrolizumab combined with pralatrexate (Arm A) or decitabine (Arm C) or decitabine and pralatrexate (Arm B) in patients with peripheral T-cell lymphoma (PTCL) and cutaneous T-cell lymphoma (CTCL). In all arms, toxicity will be assessed according to the NCI Common Toxicity Criteria for Adverse Events (CTCAE), version 5.0. Dose-limiting toxicity (DLT) is a binary outcome (yes/no) and will be determined by adverse events occurring during the first cycle of treatment (see Section 5.3 for DLT definition). In all arms, the maximum tolerated dose (MTD) is defined as the dose combination with a DLT rate closest to the target DLT rate of 25%. The study will accrue participants in cohorts of size 1 in all arms. After accrual of a participant to an arm, the accumulating DLT data will be used to update the model-based estimated DLT

probabilities for each dose level. These estimates will then be used to update the recommended dose level for the next participant accrued to that arm of the study.

Arms A and C:

The primary objectives of Arms A and C is to determine the MTD, defined by acceptable toxicity, of decitabine (Arm C) or pralatrexate (Arm A) (plus a fixed dose of pembrolizumab) from among the 3 study dose levels in the following tables, and to evaluate efficacy, as determined by overall response rate, at the estimated MTD.

Arm A		
Dose Level	Pralatrexate	Pembrolizumab*
Level 1 (start)	30 mg/m  day 1, 8, 15	200 mg day 1
Level -1	30 mg/m  day 1, 15	200 mg day 1
Level -2	20 mg/m  day 1, 15	200 mg day 1

Arm C		
Dose Level	Decitabine	Pembrolizumab*
Level 1 (start)	20 mg/m  day 1->5	200 mg day 8
Level -1	20 mg/m  day 1->3	200 mg day 8
Level -2	10 mg/m  day 1->3	200 mg day 8

Based on the accumulated data from the previous 5 subjects (1 observed DLT) accrued to Arm A, the first eligible subject in Arm A will be entered onto Level 1. Based upon the accumulated data from the previous 4 subjects (2 observed DLTs) accrued to Arm C, the first eligible subject in Arm C will be entered onto Level -1.

Arm B:

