## 10.2 Dose allocation

### Arms A and C

Dose allocation in Arms A and C will be based upon a continual reassessment method (CRM), which uses a model for the probability of DLT and the accumulated DLT data at each dose level to sequentially allocate each new patient cohort. Toxicity assessment is based on the occurrence of DLTs, and the minimum follow-up for determination of escalation is one cycle of treatment. The DLT probabilities are modeled using a one-parameter working model  $R(d_i) = \Pr(\text{DLT at dose level } i) \approx \alpha_i^{\exp(a)}$ , where  $\alpha_i$  is the skeleton of the working model. The skeleton values are pre-specified constants and were chosen according to the algorithm of Lee and Cheung, which yields a working model that results in well-performing operating characteristics in a broad range of scenarios. For this study, the skeleton values are  $\alpha_i = (0.08, 0.15, 0.25)$ . Based on the available DLT data  $D = \{(y_i, n_i); i = 1, \dots, 3\}$ , where where  $y_i$  is the number of DLT's and  $n_i$  is the number of subjects treated on study dose level  $i$ , the likelihood is given by  $L(a) \propto \prod_{i=1}^3 (\alpha_i^{\exp(a)})^{y_i} (1 - \alpha_i^{\exp(a)})^{n_i - y_i}$ .

After accrual of each patient into the trial, the DLT probability estimates,  $\tilde{R}(d_i)$ , are updated via  $\tilde{R}(d_i) = \alpha_i^{\exp(\tilde{a})}; \quad \tilde{a} = \arg \max L(a)$ .

These estimates are used to sequentially allocate patients to the dose indicated by the modeling to have the estimated DLT rate closest to 25%. The study will accrue participants in cohorts of size 1 and dose levels will not be skipped. The coherence principle will be used, where the next patient will not be treated at a dose level higher than the current dose level if the current patient experiences a DLT. Additionally, the next patient will not be treated at a dose level lower than the current dose level if the current patient does not experience a DLT. The study will sequentially repeat the estimation procedure after the enrollment and follow-up of each cohort. The allocation procedure will be repeated until sufficient information about the MTD has been obtained according to the stopping rules described below.

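### Section 10.5, Arm C: the printed safety-stop rates are about one half or one third of what the section 10.3 bounds produce, depending on whether a crossing at the tenth participant counts

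*Protocol*

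**What the plan says.** Section 10.3 stops Arm A or C for safety when the lower limit of an Agresti-Coull "binomial confidence interval (with 80% confidence) for the lowest study dose level exceeds the target DLT rate". The table headed "Stopping guidelines for DLTs at the lowest dose level" turns this into at least 2 DLTs among 2 or 3 participants, and at least 3 among 4. A note adds that "at most 4 participants can be accrued to Level -2 before the maximum sample size is reached".

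Section 10.5 says of the simulations: "The confidence level used to define the safety stopping guidelines was 80" per cent. It runs 5000 trials per scenario to a total of 10 participants per arm, and describes the last column as trials stopped early for safety. For scenarios 1, 2 and 3 that column reads 0.0, 0.24 and 1.24 in Arm A, and 0.0, 0.52 and 2.24 in Arm C. The captions give the starting data as 1 DLT in 5 (Arm A) and 1 DLT in 4 (Arm C), all on dose level 3. Section 10.1 gives Arm C as 2 DLTs in 4, with the next participant at Level -1.

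Neither section says whether a crossing produced by the tenth and last participant counts as a stop.

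**The concern.** The design is small enough to enumerate exactly: 5 further participants in Arm A and 6 in Arm C. A printed operating characteristic can therefore be checked without simulation error. The safety-stop column is the protocol's only evidence of how the Arm A and C safety rule behaves. If it is too low, readers and the monitoring committee will expect halts less often than the written rule causes them. The missed stops also reappear as selections of the lowest level as the MTD, which overstates how often the arm ends with a recommended dose.

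**Working it through.** **Inputs**
- Target (10.1): "the maximum tolerated dose (MTD) is defined as the dose combination with a DLT rate closest to the target DLT rate of 25" per cent.
- Model (10.2): one-parameter power model fitted by maximum likelihood. "For this study, the skeleton values are" 0.08, 0.15 and 0.25.
- Allocation (10.2): "The study will accrue participants in cohorts of size 1 and dose levels will not be skipped". Coherence works both ways: no escalation after a DLT, and no de-escalation after a participant without one.
- True DLT rates (10.5), lowest to highest level: scenario 2, 0.15/0.25/0.40; scenario 3, 0.25/0.40/0.55. Dose levels 1, 2 and 3 in 10.5 are Levels -2, -1 and 1 in 10.1.

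**Step 1: the bounds.** The lower limit is p̃ − z√(p̃(1−p̃)/ñ), with ñ = n + z², p̃ = (y + z²/2)/ñ and z = 1.2816 (two-sided 80%). It is 0.494 for 2/2, 0.317 for 2/3 and 0.425 for 3/4, all above 0.25. One DLT fewer gives 0.164, 0.102 and 0.230, all below. The printed bounds are correct.

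**Step 2: the model reproduces the rest of the tables.** Average numbers on dose level 3, scenarios 1/2/3:

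| Arm | Printed | Exact |
|---|---|---|
| A | 9.3 / 8.7 / 8.0 | 9.33 / 8.68 / 7.95 |
| C (1 DLT in 4) | 8.5 / 7.5 / 6.5 | 8.51 / 7.48 / 6.50 |

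Selection of levels 2 and 3 agrees within about 1.5 points. The exception is the printed 3.1 in Arm C scenario 1 (exact 30.3); that printed row sums to only 6.9 + 3.1 + 62.1 = 72.1. The 7-per-level rule was evidently off in the simulations (up to 9.3 on one level), but it does not change the stop rates.

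**Step 3: Arm C crossings, scenario 3.** Each path's probability is the product of its outcomes. For example, DLTs at level 3, level 2, level 1 and level 1 give 0.55 × 0.40 × 0.25 × 0.25 = 1.375%.

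| Participant at crossing | DLTs/treated at lowest level | Probability |
|---|---|---|
| 8 | 2/2 | 1.375% |
| 9 | 2/2 | 1.444% |
| 9 | 2/3 | 2.063% |
| 10 | 2/2 | 0.495% |
| 10 | 2/3 | 2.166% |

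The first three rows sum to 4.88%; all five sum to 7.54%. Scenario 2 gives 0.225 + 0.304 + 0.382 = 0.91%, and with 0.127 + 0.516 added, 1.55%.

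**Step 4: printed against exact.** Standard error = √(p(1−p)/5000).

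| Arm C | Printed | Exact, participant 10 not counted | Exact, counted |
|---|---|---|---|
| Scenario 2 | 0.52% | 0.91% (ratio 0.57; 2.9 SE) | 1.55% (0.34; 5.9 SE) |
| Scenario 3 | 2.24% | 4.88% (0.46; 8.7 SE) | 7.54% (0.30; 14.2 SE) |

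The closest rule found stops at 2 of 2 only and ignores participant 10: 0.53% and 2.82%. It drops the printed 2-of-3 bound and still misses scenario 3 by 2.5 SE. That the 2-of-3 bound was not applied in the simulation is a plausible inference, no more.

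**Step 5: effect on selection.** In Arm C scenario 3, lowest-level selection plus stopping is 50.1 + 2.24 = 52.3% as printed and 44.0 + 7.54 = 51.5% exactly, so about the right share of trials ends at the lowest level. The split is what fails: selection should be 46.6% (participant 10 not counted) or 44.0% (counted).

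**Step 6: Arm A.** In scenario 3, 2/2 at participant 9 has probability 1.375% and 2/3 at participant 10 has 2.063%. The stop rates in scenarios 2 and 3 are therefore 0.22% and 1.38% without participant 10, and 0.61% and 3.44% with it. Printed: 0.24% and 1.24%.

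**Step 7: Arm C from the section 10.1 data** (2 DLTs in 4, next at Level -1). Without participant 10: 2.97% and 10.90%. Counting every crossing: 3.93% and 13.84%. From this start five participants can reach Level -2 (10 − 4 − 1 = 5), although the note in 10.3 says four, so the same interval rule was extended to n = 5 (3/5 has lower limit 0.329, 2/5 has 0.179). With the printed rows only: 3.75% and 12.79%.

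**The case against.** A reader might infer that the safety-stop column is about one third of the truth in both arms. The documents do not support that for Arm A. The column is described as early stopping, and section 10.3 acts by halting accrual; after participant 10 none is left to halt. On that reading the exact Arm A values are within 0.3 and 0.8 standard errors of the printed ones. The Arm A scenario 3 lowest-level selection also fits it better: printed 41.2%, exact 41.7% without participant 10 and 39.6% with it.

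Some evidence points the other way. From the simulated Arm C start, a fourth participant at Level -2 can only be participant 10 (4 + 1 + 1 + 4 = 10), so the row for 4 participants has no function unless that participant is checked. But 10.3 says the bounds came from a web application, so the row does not show what the simulation counted. The question stays open. It does not rescue Arm C, which fails under both conventions.

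Two further objections have some force. The section 10.1 starting data are a separate inconsistency and should not be used to enlarge the gap between the printed rates and the bounds. And the practical stakes are limited: section 10.6 calls the bounds non-binding, the written rule is unaffected, it stops at least as often as printed, and the monitoring committee reviews all adverse events and meets monthly.

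It might also be argued that Arms A and C are finished, since Arm B was to open only after them and already has 4 participants. Section 10.4 still plans additional participants in both arms, so the document does not establish this.

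**Conclusion.** The point holds for Arm C. From the start the protocol says it simulated, the printed 0.52% and 2.24% are roughly one half of the rates the section 10.3 bounds give if tenth-participant crossings are excluded (0.91% and 4.88%), and roughly one third if they are included (1.55% and 7.54%). In scenario 3 neither gap can be simulation noise. The 50.1% lowest-level selection there is overstated by 3.5 points (50.1 − 46.6) or 6.1 points (50.1 − 44.0).

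Arm A is about one third of the exact values (0.61% and 3.44%) only if tenth-participant crossings count, so no error is shown there; what is missing is the convention.

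As a distinct matter, from the Arm C data in section 10.1 the stop rates would be about 3.0–3.9% and 10.9–13.8%. The upper ends assume that participant 10 counts and that the same interval rule applies at n = 5.

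All of this rests on the model, skeleton, coherence and no-skipping rules as written in 10.2. The agreement in average numbers supports that these were the ones simulated. Nothing here suggests that the bounds themselves are wrong or that participants are less protected than the rule provides.

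**What to change.** Reconcile the Arm C starting data between sections 10.1 and 10.5. Re-run the Arm C table from the reconciled data with the section 10.3 bounds, and replace the stop-rate and selection cells, including the 3.1 in scenario 1. State in 10.3 and 10.5 whether a crossing at the tenth participant counts, and apply the same convention to Arm A; if it counts, the Arm A stop-rate and lowest-level selection cells change too. If the reconciled Arm C start is the one in 10.1, the note limiting Level -2 to four participants and the bounds table also need a row for five. The cost is a re-run of existing code, a few table cells and one or two sentences. The design does not change.
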